10.3. Statistical Analyses

10.3.1. General Statistical Considerations

Statistical analysis of this study will be the responsibility of Lilly or its designee. Any change to the data analysis methods described in the protocol will require an amendment ONLY if it changes a principal feature of the protocol. Any other change to the data analysis methods described in the protocol, and the justification for making the change, will be described in the statistical analysis plan (SAP) or the clinical study report (CSR). Additional exploratory analyses of data will be conducted, as deemed appropriate.

The primary analysis is for the treatment period up through Week 16.

Efficacy analyses will be conducted on all randomized patients according to the treatment the patients are assigned. The analyses for the primary and multiplicity-adjusted objectives will be performed for the efficacy estimand including data collected prior to permanent discontinuation of IP and for the ITT estimand including all data collected through Week 16 regardless of IP use (Section 10.3.3.1). Unless otherwise specified, the efficacy analyses for other secondary objectives and exploratory objectives will be performed for the efficacy estimand. When change from baseline is included as a response variable of analysis models, the patient will be included in the analysis only if a baseline and a postbaseline measurement are available.

Safety analyses will be conducted on the Safety population. Analyses of AEs will include 2 sets of analyses, unless otherwise specified. The first set of analyses will include data collected prior to permanent discontinuation of IP. The second set of analyses will include all data collected during the course of the entire study including the follow-up visit, regardless of IP use. Analyses of hypoglycemia will be conducted on data collected prior to permanent discontinuation of IP, while analyses for post-treatment may be conducted as needed. Analyses of safety laboratory measurements will be performed on all data collected during the planned treatment period regardless of IP use.

Unless otherwise noted, all tests of treatment effects will be conducted at a 2-sided alpha level of 0.05, and CIs will be calculated at 95%, 2-sided. All tests of interactions between treatment groups and other factors will be conducted at a 2-sided alpha level of 0.10. Countries in similar geographic regions with fewer than 10 patients, based on the all-randomized population, will be

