5.2. Determination of Sample Size

Approximately 420 patients will be randomized in order that approximately 368 patients complete the study through the primary endpoint at Week 16.

[figure not shown]
The primary objective of this study is to test the hypothesis that LY900014 is noninferior to Humalog on glycemic control as measured by change from baseline to Week 16 in HbA1c in patients with T1D when administered in a double-blind manner using CSII with bolus doses delivered 0 to 2 minutes prior to the meal.

Patients will be randomized in a 1:1 ratio to double-blind LY900014 with bolus dose delivered 0 to 2 minutes before meals or double-blind Humalog with bolus doses delivered 0 to 2 minutes before meals. Assuming a noninferiority margin (NIM) of 0.4%, no true difference between treatment groups, and a standard deviation (SD) of 0.88%, 368 completers (184 in each treatment group) will provide at least 99% power to show noninferiority between LY900014 and Humalog in change from baseline to Week 16 in HbA1c using the upper limit of a two-sided 95% confidence interval (CI) (LY900014 – Humalog). Assuming a 12% dropout rate for 16 weeks, approximately 420 patients will need to be randomized. This sample size also has 90% power to show noninferiority between LY900014 and Humalog using a 0.3% NIM at Week 16.

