Health outcomes: ITSQ, EQ-5D-5L, EQ-VAS	All Randomized Patients with a baseline and a post-baseline observation	Last of Visits 2-4 prior to initiation of IP	Last of Visits 5-13 prior to discontinuation of IP
Safety Laboratory Tests (chemistry, hematology) – continuous analysis	All Patients in the Safety Population with a baseline and a post-baseline observation	Visit 1	Visit 13 (planned) AND last of Visits 5-13 (planned including early discontinuation visits) regardless of IP use
Safety Laboratory Tests (chemistry, hematology) – categorical analysis	All Patients in the Safety Population with a normal baseline (with respect to the direction being analyzed) and a post-baseline observation	Visits 1-4 (including unplanned tests)	Visits 5-13 (including unplanned tests) regardless of IP use
TEAEs	All Patients in the Safety Population	Prior to first dose of randomized IP (or Visit 4 date if the dose date is missing) but after the first dose of open-label insulin lispro in the Lead-in Period	From first dose of randomized IP to last dose of randomized IP AND From first dose of randomized IP to Visit 801
Hypoglycemia events	Safety Population	All Visits 2-4	All Visits 5-13 prior to discontinuation of IP
Unplanned infusion set changes	Safety Population	All Visits 2-4	All Visits 5-13 prior to discontinuation of IP
Weight and vital signs	All Patients in the Safety Population	Last of Visits 2-4	Visits 5-13 prior to discontinuation of IP

	with a baseline and a post-baseline observation		
Anti-insulin lispro antibodies	Safety Population	Visit 4	Visits 5-801 regardless of IP use

Abbreviations: 1,5-AG = 1,5-Anhydroglucitol; AIT = active insulin time; ANCOVA = analysis of covariance; CR = carbohydrate ratio; EQ-5D-5L = European Quality of Life – 5 Dimensions 5 Level; EQ-VAS = EuroQol visual analogue scale; HbA1c = hemoglobin A1c; IP = investigational product; ISF = insulin sensitivity factor; ITSQ = Insulin Treatment Satisfaction Questionnaire; ITT = intention-to-treat; LOCF – last-observation-carried forward; MMTT = mixed meal tolerance test; MMRM = mixed-effect model repeated measures; PPG = postprandial glucose; SMBG = self-monitored blood glucose; TEAE = treatment-emergent adverse event.

¹ If the percentage of the patients with missing MMTT data at baseline is higher than 15%, a constrained longitudinal data analysis model (Liu et al. 2009; Lu 2010) will be used instead. See Section 6.11.2.

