6.12.3. Hypoglycemic Events and Other Adverse Events

6.12.3.1. Hypoglycemic Events

Hypoglycemia events that occur during the study will be captured using a paper diary starting from Visit 2 through Visit 801. Whenever hypoglycemia is suspected ($BG \leq 70 \text{ mg/dL}$ [3.9 mmol/L]), the patient should record the BG value, any associated symptoms, and the treatment administered. A set of events is counted as 1 event in analysis if the duration between adjacent events is ≤ 30 minutes.

The event with the highest severity will be selected for analysis with severity determined in the order of: 1) it is a severe hypoglycemia, 2) it has symptoms of hypoglycemia reported, and 3) it has the lowest blood glucose value. If there are multiple events tied in all 3 aspects, the event with the largest number of non-missing responses to the questions of nocturnal hypoglycemia and postmeal time frame will be selected. Hypoglycemia rates will be summarized for periods of 1 year and 100 years (severe hypoglycemia only). The rate of severe hypoglycemia per 100 years will be compared between treatment groups using the empirical method (see [Appendix 1](#) for details). For each of other categories of hypoglycemia, the number of hypoglycemia events during 0 to 16 weeks (rate) after randomization will be analyzed by using a negative binomial regression model including treatment. An offset defined as the log transformation of treatment exposure in the specific period (days)/365.25 days will be included in the model to estimate the rate of hypoglycemia per year. The proportion of patients with at least 1 hypoglycemic event in each category (incidence) during 0 to 16 weeks after randomization will be analyzed using a logistic regression model including treatment.

The following types of hypoglycemia events will be derived in the analysis data sets: documented hypoglycemia, severe hypoglycemia, nocturnal hypoglycemia, and non-nocturnal (daytime) hypoglycemia. Only severe hypoglycemia will be collected as AEs and all episodes of severe hypoglycemia will be considered as SAEs. Documented hypoglycemia will be based on $BG \leq 70 \text{ mg/dL}$ and $BG < 54 \text{ mg/dL}$.

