[Table ITRO 6.3](#) provides detailed statistical methods for each endpoint related to hypoglycemia. For these analyses, hypoglycemia events prior to the discontinuation (i.e., last dose) of IP will be summarized. Additional analyses for other types of hypoglycemic events not mentioned in the table may be conducted as needed.

A listing of patients with at least 1 severe hypoglycemia reported (as SAE) after randomization (including Visit 801) will be provided.

A list of MedDRA PTs will be used for the narrow search of potential severe hypoglycemia in spontaneously reported AEs. The events identified through the search strategy that are also reported as SAEs will be summarized and compared between treatments. Fisher's exact test will be used to assess the treatment difference in the proportion of patients with potential severe hypoglycemia.

Table ITRO 6.3. Summary of Analyses for Endpoints Related to Hypoglycemia

Endpoint	Analysis Period ^b	Statistical Method
Rate of hypoglycemic events (per patient per year) 
 • All Documented^a • Nocturnal^a • Non-Nocturnal (or Daytime) (Documented and between waking and bedtime)^a 	0-16 weeks	Negative binomial regression with treatment and log (exposure/365.25 days) as the offset in the model.
Incidence of hypoglycemic events 
 • All Documented^a • Nocturnal^a • Non-Nocturnal (or Daytime) (Documented and between waking and bedtime)^a 	0-16 weeks	Logistic regression with treatment
Rate of post-meal hypoglycemic events (per patient per year) 
 • All Documented^a 	$\leq 1, \leq 2, \leq 4$, and >2 to ≤ 4 , and >4 hours after start of a meal within 0-16 weeks	Negative binomial regression with treatment and log (exposure/365.25 days) as the offset in the model.
Incidence of post-meal hypoglycemic events 
 • All Documented^a 	$\leq 1, \leq 2, \leq 4$, and >2 to ≤ 4 , and >4 hours after start of a meal within 0-16 weeks	Logistic regression with treatment
Rate of severe hypoglycemic events (per patient per 100 years)	0-16 weeks	Exposure adjusted rate per 100 years (calculated by total number of events divided by total exposure for individual patients) will be provided and the empirical method (see Appendix 1 for details) will be used for treatment comparison.

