Incidence of severe hypoglycemic events	0-16 weeks	The treatment comparison will be based on a logistic regression model with treatment as a covariate.

^a All documented hypoglycemia and the subcategories based on the thresholds of BG ≤ 70 mg/dL and BG < 54 mg/dL will be analyzed.

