The meal time will be collected in the database by eCRF both for the MMTT and non-MMTT meals. The non-MMTT meals include all outpatient meals including morning (breakfast), midday (lunch) and evening (dinner) meals and overall (across the 3 meals). For the non-MMTT meals, only the first meal marker time will be used for each category (breakfast, lunch or dinner). Any data collected after the next meal (regardless of the category of the next meal) will be censored for the analysis with regards to the current meal. No outcome variables will be derived for bedtime meal but its time will be used to censor the data when deriving outcome variables for dinner. Time in ranges by meal will be derived for 0 to 1 hour, 0 to 2 hours, 0 to 3 hours and 0 to 4 hours after the start of each meal while variability by meal will only be derived for 0-4 hours.

All continuous variables will be analyzed using a similar MMRM model as used for the primary endpoint. If the percentage of patients with baseline missing (potentially due to missing meal event markers) is greater than 20% for any meal, a constrained longitudinal data analysis (cLDA) will be performed for all PPG-related CGM endpoints for that meal with treatment, strata (pooled country and patient's personal CGM use during the study), visit, and 2 dummy variables

to indicate treatment effect of LY90014 relative to Humalog at Visit 10 and Visit 13, respectively. An unstructured covariance structure will be used to model the within-patient errors. Significance tests will be based on LS means and Type III tests. SAS PROC MIXED will be used to perform the analysis. If this analysis fails to converge, the same order of the covariance structures will be tested as specified in Section 6.11.1.

Hypoglycemia/hyperglycemia rate per year as measured by CGM data will be analyzed using a negative binomial regression model with treatment as a covariate and an offset defined as the log transformation of days of CGM use/365.25 days. The proportion of patients with at least 1 hypoglycemia/hyperglycemia event as measured by CGM data (incidence) will be analyzed using a logistic regression model with treatment in the model. Similarly, proportion of patients who have achieved the guidance (Battelino 2019) recommended CGM targets of glycemic control (Table ITRO.6.6) during the 14 to 16 weeks of the treatment period will be summarized by treatment and analyzed using the same analysis methods.

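### Hypoglycemia incidence over 0-16 weeks scores a patient who stops IP before a first event as event-free for 16 weeks; add a time-to-first-event comparison

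*SAP*

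**What the plan says.** - **Incidence model.** SAP 6.12.3.1 gives the comparison as "incidence) during 0 to 16 weeks after randomization will be analyzed using a logistic regression model including treatment". Table ITRO 6.3 repeats it for documented, nocturnal, daytime and post-meal events. For severe events the table says: "The treatment comparison will be based on a logistic regression model with treatment as a covariate". No exposure term appears in any of these models.
- **Events counted.** SAP 6.12.3.1: "For these analyses, hypoglycemia events prior to the discontinuation (i.e., last dose) of IP will be summarized". Table ITRO 6.2 sets the window at "All Visits 5-13 prior to discontinuation of IP". Protocol 10.3.1 agrees: "Analyses of hypoglycemia will be conducted on data collected prior to permanent discontinuation of IP". Analyses of later data are left to be done if needed.
- **Denominator.** Table ITRO 6.2 uses the Safety Population, which Table ITRO 6.1 defines as every randomized patient with at least one dose of IP, however long the exposure.
- **Rate models.** In the same section and table, the negative binomial models carry log(exposure/365.25 days) as an offset, and the severe-event rate divides by total exposure.
- **Standing of the endpoint.** Incidence is named together with rate in endpoints 8 (post-meal) and 9 (documented) of Table ITRO 4.1. Severe-event incidence appears only in Table ITRO 6.3, because endpoint 7 is a rate.

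Neither document plans a time-to-first-event analysis of hypoglycemia. SAP 6.12.1 only summarizes exposure.

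**The concern.** The event window closes when the patient stops IP, but the outcome is read as yes or no over 16 weeks. Someone who stops at Week 2 without an event carries the same weight as someone followed event-free to Week 16. The rate models beside it allow for this; the incidence models do not.

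Two things follow. The incidence that patients would show over 16 weeks on IP is understated in both arms. And if stopping is more frequent or earlier in one arm, that arm shows fewer patients with events for that reason alone. In a safety comparison this can hide a real excess in the arm with more stopping. Protocol 5.5 itself raises early post-meal hypoglycemia as a possible risk of LY900014, and endpoint 8 includes its incidence.

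**Working it through.** **Inputs from the documents.** SAP 5.2: "Assuming a 12% dropout rate for 16 weeks, approximately 420 patients will need to be randomized". Check: 368/(1 - 0.12) = 418.2, or 419 when rounded up, which agrees with about 420, or 210 per arm. The stated HbA1c power also reproduces with 184 per arm and SD 0.88%: 99.2% at a margin of 0.4% and 90.5% at 0.3%. The documents give no figure for hypoglycemia incidence and no split of stopping by arm.

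**Assumptions.** True 16-week incidence p, the same in both arms; constant hazard; a share d stops IP at times uniform over the 16 weeks, unrelated to risk. The split 16% against 8% averages the planned 12%.

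**Formulas.** With L = -ln(1 - p), a stopper has an event before stopping with probability s = 1 - p/L. Observed incidence = (1 - d)p + d·s.

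**Worked case, p = 50%.** L = 0.6931; s = 1 - 0.5/0.6931 = 0.2787.
- d = 16%: 0.84 × 0.5 + 0.16 × 0.2787 = 46.5%.
- d = 8%: 0.92 × 0.5 + 0.08 × 0.2787 = 48.2%.
- OR = (0.4646/0.5354)/(0.4823/0.5177) = 0.93.
- Balanced 12%: 0.88 × 0.5 + 0.12 × 0.2787 = 47.3% in both arms. OR = 1.00, but both arms fall below the true 50%.

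**Other incidences, 16% against 8%.**

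| True incidence | s | Observed | OR |
|---|---|---|---|
| 10% | 0.0509 | 9.2% vs 9.6% | 0.955 |
| 50% | 0.2787 | 46.5% vs 48.2% | 0.93 |
| 70% | 0.4186 | 65.5% vs 67.7% | 0.90 |

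**If patients differ in risk.** The negative binomial rate model already implies that they do. Take gamma frailty with variance 2 (assumed), so that event-free survival is (1 + kt)^(-1/2), with t the fraction of 16 weeks and k = (1 - p)^(-2) - 1.
- p = 50%: k = 3; s = 1 - (2/3)(2 - 1) = 0.333; observed 47.3% vs 48.7%; OR 0.95.
- p = 70%: k = 10.11; s = 1 - (2/10.11)(3.333 - 1) = 0.538; observed 67.4% vs 68.7%; OR 0.94.

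**If stopping is earlier.** With constant hazard and every stop at Week 4, s = 1 - (1 - p)^(1/4). At p = 50%, s = 0.159 and the observed figures are 44.6% vs 47.3%, OR 0.90. At p = 10% the OR is 0.93.

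**Effect on the test (210 per arm, constant hazard, uniform stopping).** With no true difference, the chance of a significant result is 5.2% at 10% incidence and 6.5% at 50%. At 50% incidence, power for a true hazard ratio of 1.3, with the higher risk in the arm that stops more, is 45% with 12% stopping in each arm and 31% with 16% against 8%.

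**Check of remedies.** In simulation with no true difference and patients differing in risk, Cox regression censored at the stop gave hazard ratios of 0.99-1.00 and equal Kaplan-Meier incidence in the two arms. A complementary log-log model with a log-exposure offset was unbiased under constant hazard, but drifted to 1.02-1.05 at 70-90% incidence when risks differed.

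**The case against.** **Exposure-adjusted rates are already planned.** Every diary category with an incidence comparison also has a rate comparison adjusted for exposure. SAP 6.6 compares reasons for stopping treatment by arm, and SAP 6.12.1 tabulates exposure in 4-week bands, so an imbalance would be seen. This stands as mitigation. It does not repair the incidence comparison, which is a separate part of endpoints 8 and 9, and a rate can be driven by a few patients with many events.

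**Crude on-treatment incidence is a legitimate description.** SAP 6.12.2 handles adverse events in the same way, the logistic model is in Protocol 10.3.4, and these endpoints lie outside the multiplicity-controlled set. This also stands, and it is the reason to keep the crude analysis and add to it.

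**The bias between arms needs an imbalance.** A reader might infer that the plan favours LY900014. The documents do not support that: they give no stopping by arm, the trial is double-blind, and the 12% is study dropout, which may differ from IP stopping because patients who stop IP are asked to stay in follow-up (Protocol 8.1).

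**Not every early stopper is misclassified.** A reader might infer that all of them count as event-free. A patient with an event before stopping counts as an event; only those without one are affected.

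**CGM incidence.** The SAP 6.13 model has the same form ("event as measured by CGM data (incidence) will be analyzed using a logistic regression model with treatment in the model"), so a reader might extend the point to it. That analysis is derived by CGM session rather than over 0-16 weeks, is not the incidence in endpoints 8 and 9, and could be sized only with invented counts of valid days. The point is confined to diary events.

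**Conclusion.** The point holds for the diary-based incidence comparisons. On-IP events, a full Safety Population denominator and a treatment-only logistic model together score event-free early stoppers as 16-week non-events. Incidence over 16 weeks on IP is understated in both arms (for example 47.3% in place of 50% with 12% stopping), and unequal stopping tilts the comparison towards the arm with more or earlier stopping.

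The size is modest. At 16% against 8% and uniform stop times, the OR under no true difference is about 0.95 at 10% incidence and 0.90 to 0.95 at 50-70%, the upper end applying when patients differ in risk. Stopping concentrated early makes it somewhat larger. With stopping balanced in amount and timing there is no between-arm bias. The incidences, the split and the stop times are all assumptions. The planned rate analyses lessen the consequence, so this is a gap worth closing; it does not undermine the safety evaluation as a whole.

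**What to change.** In SAP 6.12.3.1 and Table ITRO 6.3, for documented and post-meal events (objectives 8 and 9), their subcategories in the table, and severe events:

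- add a comparison of time to first event, censored at last IP dose, by log-rank test or Cox model;
- report Kaplan-Meier incidence at Week 16 by arm;
- keep the crude percentages and the protocol's logistic model alongside.

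The SAP should say how the censoring date relates to its general rule in 6.1, which counts diary entries up to one day after the last dose as on IP.

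A complementary log-log model with an exposure offset is not the preferred remedy, because it assumes a hazard that is constant over time and the same for all patients.

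The cost is one more analysis per category, from event and last-dose dates that the plan already uses. The added analysis assumes that stopping IP is unrelated to hypoglycemia risk; if patients stop because they are prone to hypoglycemia, some bias remains. Because the logistic model stays, the protocol's method is supplemented and not replaced, and Protocol 10.3.1 allows such a change to be described and justified in the SAP.

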9.4. Safety

9.4.1. Hypoglycemia

Patients will be required to perform SMBG when hypoglycemia is suspected through

- symptoms experienced,
- personal CGM or FGM readings, or
- a perceived increased risk as related to
 - dietary intake,
 - physical activity, or
 - inadvertent or atypical insulin dosing.

All patients will be instructed to treat a BG ≤ 70 mg/dL (3.9 mmol/L) as hypoglycemia.

If a hypoglycemia event is suspected, the patient should record the BG value, any associated symptoms, and the treatment administered in the study diary. The patient should contact the site as necessary. All hypoglycemia events (severe and nonsevere) must be reported on the hypoglycemia eCRF. All episodes of severe hypoglycemia must be confirmed by the investigator and then reported as SAEs on the AE eCRF page and on the SAE eCRF page. Episodes of hypoglycemia not meeting the criteria for severe hypoglycemia should not be reported as an AE.

Hypoglycemia will be described using the following definitions:

- **Documented Glucose Alert; BG ≤ 70 mg/dL (3.9 mmol/L):**
 - Documented symptomatic hypoglycemia: an event with typical symptoms of hypoglycemia.
 - Documented asymptomatic hypoglycemia: an event without typical symptoms of hypoglycemia.
 - Documented unspecified hypoglycemia: with no information about symptoms of hypoglycemia available (this has also been called unclassifiable hypoglycemia).
- **Documented Clinically Significant Hypoglycemia with similar criterion as above except for threshold BG < 54 mg/dL (3.0 mmol/L)**
 - Documented symptomatic hypoglycemia

- Documented asymptomatic hypoglycemia
- Documented unspecified hypoglycemia
- **Probable Symptomatic Hypoglycemia:** an event during which symptoms are present, but BG measurement was not reported.
- **Severe Hypoglycemia:** during these episodes, patients have an altered mental status and cannot assist in their own care, may be semiconscious or unconscious, or experience coma with or without seizures, and the event requiring assistance of another person to actively administer carbohydrate, glucagon, or other resuscitative actions. Blood glucose measurements may not be available during such an event, but neurological recovery attributable to the restoration of BG concentration to normal is considered sufficient evidence that the event was induced by a low BG concentration (BG ≤ 70 mg/dL [3.9 mmol/L]).
- **Other Hypoglycemia**

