 - **Nocturnal Hypoglycemia:** any documented hypoglycemic event (including severe hypoglycemia) that occurs between bedtime and waking.
 - **Overall (or Total) Hypoglycemia:** this category combines all cases of hypoglycemia (documented hypoglycemia and probable symptomatic hypoglycemia, including severe hypoglycemia) excluding the events of relative hypoglycemia. Nocturnal and severe hypoglycemia are special cases of documented or probable hypoglycemia. If an event of hypoglycemia falls into multiple subcategories, the event is only counted once in this category.

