10.3.4. Safety Analyses

Safety measures will include AEs, hypoglycemia, unplanned infusion set changes and reasons, vital signs and weight, treatment exposure, laboratory measures, and antibodies to insulin lispro.

Events that are newly reported after the first dose of IP or reported to worsen in severity from baseline will be considered TEAEs. The Medical Dictionary for Regulatory Activities (MedDRA) lowest level term (LLT) will be used in the treatment-emergent assessment. The maximum severity for each LLT during the baseline period will be used as baseline severity.

SAEs, AEs reported as reason for discontinuation from the IP or study, and TEAEs will be summarized in tables using the MedDRA PT, sorted by decreasing frequency within the LY900014 treatment group. TEAEs will also be summarized by PT sorted by decreasing frequency within SOC for all TEAEs and by maximum severity. For events that are specific to only one sex, the denominator and computation of the percentage will include only patients from the given sex. The number and proportion of patients with at least 1 event for each type of event will be summarized and compared between treatment groups using Fisher's exact test. Serious adverse events, AEs reported as reason for discontinuation from the study, and TEAEs will be summarized for open-label Humalog during the lead-in period.

Hypoglycemia rates will be summarized for periods of 1 year and 100 years (severe hypoglycemia only). The rate of severe hypoglycemia per 100 years will be compared between treatment groups using the empirical method (details will be described in the SAP). For each of other categories of hypoglycemia, the number of hypoglycemia events during a specific period (rate) after randomization (for example, 0 to 4 weeks of treatment period) will be analyzed by using a negative binomial regression model including treatment. An offset defined as the log transformation of treatment exposure in the specific period (days)/365.25 days will be included in the model to estimate the rate of hypoglycemia per year. The proportion of patients with at least 1 hypoglycemic event in each category (incidence) during a specific period after randomization will be analyzed using a logistic regression model including treatment.

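### SAP Table ITRO 6.3 omits the protocol's probable symptomatic and overall hypoglycemia categories, so a non-severe symptomatic event without a glucose value enters no prespecified between-arm analysis of reported events

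*SAP*

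**What the plan says.** Protocol 9.4.1 sets out the hypoglycemia categories. Documented events are defined at two glucose thresholds (at or below 70 mg/dL, and below 54 mg/dL), and each is split by symptom status, for example "Documented symptomatic hypoglycemia: an event with typical symptoms of hypoglycemia". Probable symptomatic hypoglycemia is a separate category: "an event during which symptoms are present, but BG measurement was not reported". Overall hypoglycemia is defined so that "this category combines all cases of hypoglycemia (documented hypoglycemia and probable symptomatic hypoglycemia, including severe hypoglycemia"; an event that fits several subcategories is counted once. Nocturnal hypoglycemia is "any documented hypoglycemic event (including severe hypoglycemia) that occurs between bedtime and waking".

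Protocol 10.3.4 gives severe hypoglycemia its own empirical rate method and then plans negative binomial regression for the rest: "For each of other categories of hypoglycemia, the number of hypoglycemia events during a specific period (rate) after randomization". Incidence in each category is to be analysed by logistic regression.

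SAP 6.12.3.1 repeats those models, but the event types to be derived are "documented hypoglycemia, severe hypoglycemia, nocturnal hypoglycemia, and non-nocturnal (daytime) hypoglycemia". Table ITRO 6.3 lists all documented, nocturnal, daytime, post-meal documented and severe events. Its daytime row reads "Non-Nocturnal (or Daytime) (Documented and between waking and bedtime", and its footnote subdivides by glucose level: "All documented hypoglycemia and the subcategories based on the thresholds of BG". The SAP text before the table says that other event types can be analysed if needed, without naming any.

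**The concern.** The protocol recognises a kind of reported event that has symptoms but no glucose value, and it defines an overall category that includes it. The SAP names neither category and does not explain why. Protocol 10.3.1 and SAP 6.1 both say that a change from the protocol's analysis methods, with its justification, will be described in the SAP or the clinical study report.

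The possible cost is in safety. Protocol 5.5 says that the better post-meal glucose seen with LY900014 might bring more early postprandial hypoglycemia. A patient who feels symptoms and treats without testing produces a probable symptomatic event. If such events differed between arms, no prespecified table of reported hypoglycemia would show it.

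**Working it through.** The point rests on definitions, and the documents state no figure to reproduce. The check has three steps.

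**1. Classify each kind of reported event under the SAP rules.** Documented means a glucose value at or below 70 mg/dL. Nocturnal events are documented by the protocol definition, and daytime events by the SAP table. The values 65 and 50 mg/dL are examples from the two threshold bands.

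| Glucose value | Severe? | Planned comparative category |
|---|---|---|
| Missing | No (day or night) | None |
| Missing | Yes (day or night) | Severe |
| 65 mg/dL | No | Documented (≤70), plus nocturnal or daytime |
| 65 mg/dL | Yes | As above, plus severe |
| 50 mg/dL | No | Documented (≤70 and <54), plus nocturnal or daytime |
| 50 mg/dL | Yes | As above, plus severe |

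The post-meal rows are limited to documented events, so they add nothing for the first line of the table. That line, when symptoms are present, is the protocol's probable symptomatic category without its severe cases.

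**2. Look for another route into a between-arm comparison.**

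- Adverse events: Protocol 9.4.1 says that non-severe hypoglycemia is not to be reported as an adverse event, so the adverse event tables do not pick it up.
- MedDRA term search (SAP 6.12.3.1): the comparison covers only events also reported as serious adverse events.
- CGM episodes (SAP 6.13, Table ITRO 6.5): these are compared between arms on duration, rate and incidence, with post-meal windows. They count sensor readings, not reported events, and exist only during blinded sessions. After randomization there are two 14-day sessions, before Visits 10 and 13. That is 2 × 14 = 28 days out of 16 × 7 = 112, or 28/112 = 25% of the treatment period. This is nominal coverage, before any missing sensor data.

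**3. Check the rule for events close in time.** SAP 6.12.3.1 merges events no more than 30 minutes apart and keeps one. It ranks by severe status, then reported symptoms, then lowest glucose. Take an asymptomatic reading of 62 mg/dL within 30 minutes of a non-severe symptomatic event with no reading. The symptomatic record is kept. Unless the discarded glucose value is carried over, which the SAP does not say, the pair then leaves the documented count. This is a side effect; the conclusion does not depend on it.

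**The case against.** Much of the case on the other side stands.

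- A reader might infer that the SAP has dropped an endpoint. It has not. Objectives 7, 8 and 9 concern severe, documented post-meal and documented hypoglycemia. They are the same in both documents, and Table ITRO 6.3 covers all three.
- A reader might infer that documented symptomatic events are lost as well. They are not: every one is counted under all documented hypoglycemia, and only a separate breakdown by symptoms is absent.
- A reader might infer that these events escape every hypoglycemia analysis. That goes too far, because the CGM analyses can register an untested low during a blinded session.
- The risk named in Protocol 5.5 is already targeted for documented events. There are post-meal rate and incidence rows at several time windows and both glucose thresholds, and CGM post-meal episodes as well.
- Patients must test when they suspect hypoglycemia (Protocol 9.4.1), which should limit the number of events without a value. The protocol nevertheless defines a category for them.
- Protocol 10.3.4 refers to categories without listing them or citing 9.4.1, so the commitment is less explicit than it could be. Still, 9.4.1 is where the protocol defines its hypoglycemia categories, and the SAP offers no other reading.

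The sentence allowing other event types to be analysed does not close the gap. It commits to no category, and the types concerned are not among those to be derived.

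**Conclusion.** The concern holds in a limited form. Set against Protocol 9.4.1 and 10.3.4, the SAP omits probable symptomatic and overall hypoglycemia from its derived types and comparisons and does not say why. A non-severe symptomatic event without a glucose value is therefore in no prespecified between-arm analysis of reported events, and the CGM analyses are only a partial substitute. The primary, multiplicity-adjusted and named secondary analyses are unaffected.

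The size cannot be computed, because neither document gives the share of events without a glucose value. A reader might try an illustration. Let s be the share of Humalog-arm events that lack a value, suppose LY900014 doubles those events, and hold the rest equal. The overall rate ratio is then (1 − s) × 1 + s × 2 = 1 + s, which is 1.05 at an assumed s of 5% and 1.20 at 20%, while the documented tables show 1.00. The documents support neither the 5% to 20% range nor a doubling confined to untested events, so this shows how the omission works and is not an estimate of bias.

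Nor do the documents show a breach of the rule on justifying changes. The reason may be given in the clinical study report, which is not available here. What can be said is that the SAP itself gives none.

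**What to change.** Add overall hypoglycemia and probable symptomatic hypoglycemia, as Protocol 9.4.1 defines them, to the derived event types in SAP 6.12.3.1 and to Table ITRO 6.3. Report rate and incidence over 0 to 16 weeks with the negative binomial and logistic models already specified, counting each event once in the overall category. A documented symptomatic breakdown at the two thresholds is optional. It would help to add a sentence on how the 30-minute rule treats a symptomatic record with no glucose value.

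The cost is a few derived flags and table rows. No new data are needed: Protocol 9.4.1 already has patients record glucose values and symptoms in the diary and sends all hypoglycemia events to the hypoglycemia eCRF.
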